12.1 Assessments

Table 2. SParky Samba Outcome Assessments

Construct	Measure	Time to complete	Time points
Motor	UPDRS III: We will use section III of the Unified Parkinsons Disease Rating Scale to assess global motor function in participants	15 min	Baseline and 12 weeks
	Freezing of Gait questionnaire (FOG) : this is a patient self report measure designed to assess the severity of gait freeing in people with PD.	5 min	Baseline and 12 weeks
	Dresden Falls Questionnaire — this is a patient report questionnaire designed to assess the risk and severity of falls, a common symptom in people with PD.	5 min	Baseline and 12 weeks
	MiniBEST Test in this assessment participants are assessed across dynamic balance, functional ability and gait.	15 minutes	Baseline and 12 weeks
	Physical Activity in the Elderly (PASE) questionnaire this questionnaire is designed to capture the level of physical activity across a range of usual activities over the past 7 days.	5 min	Baseline and 12 weeks
Cognitive	Montreal Cognitive Assessment (MoCA) – we will use the truncated on- line version of the MoCA, known as Expresso, to assess cognitive function in participants. This is well validated for assessing cognitive function in pe	6 minutes	Baseline and 12 weeks
Quality of Life	Parkinson's Disease Quality of Life Questionnaire [8 items] – PDQ-8; This is a self-completion participant reported outcome designed to address aspects of functioning and well-being for those affected by Parkinson's disease. The PDQ-8 asks one question from each of the domains of the longer PDQ-39; activities of daily living, attention and working memory, communication, depression, quality of life and social relationships.	5 minutes	Baseline and 12 weeks
Self Efficacy	Oxford Participant and Activities Questionnaire (OxPaq)— this is a validated self-report questionnaire designed to assess the degree of activity and participation of those with chronic conditions taking part in community based interventions	5 minutes	Baseline and 12 weeks
	The Lorig Self Efficacy (scale will be utilised to measure self-efficacy related to exercise (exercise sub-scale only)	5 minutes	Baseline and 12 weeks

Figure 3. Schedule of enrolment, interventions and assessments

Procedures	Visits (insert visit numbers as appropriate)

	Baseline V	isit (week 0)	Intervention	Follow Up Visit (week 12 ± 5 days)			
	At home (Day -3;	At hospital (Day 0)	Delivery (Day 0 – Day 84)	At home (Day 85	At hospital Day 88 ±2		
	± 2 days)			±5 days)	days)		
Informed consent	х						
Demographics	х						
Medications		х					
Hoen and Yahr		х					
staging							
Randomisation		х					
Delivery of			X				
intervention			^				
Intervention			X	x			
Adherence							
UPDRS		х			х		
FoG	х			х			
MiniBEST		х			х		
DREFAQ	х			x			
MoCA [Espresso]		х			х		
PDQ-8	Х			Х			
OxPAQ	Х			х			
Lorig	X			x			
PASE	Х			Х			
Adverse event assessments			х	х	х		

Process Evaluation			
questionnaire		X	

12.2 Follow-up

No follow up of patients after their 12-week assessment will take place.

The follow-up period will be 12 weeks in line with completion of the primary endpoint. There will be a four week window beyond this timepoint to allow for the completion of measures relating to the process evaluation.

13 Safety Reporting

The PI is responsible for ensuring that all site staff involved in this trial are familiar with the content of this section.

All Serious Adverse Events (SAEs) that meet requirements of an SAE must be reported immediately (and within 24 hours of knowledge of the event) by the PI at the participating site to the CTR Trial team unless the SAE is specified as not requiring immediate reporting (see section 13.2).

13.1 Definitions

Term	Definition								
Adverse Event (AE)	Any untoward medical occurrence in a participant or clinical trial participant administered an intervention which are not necessarily caused by or related to that product								
Serious Adverse Event	Any adverse event that -								
(SAE)	Results in death								
	Is life-threatening*								
	 Required hospitalisation or prolongation of existing hospitalisation** 								
	Results in persistent or significant disability or incapacity								
	Consists of a congenital anomaly or birth defect								

	Other medically important condition***
Serious Adverse Reactions (SARs)	Any SAE occurring in a clinical trial participant for which there is a reasonable possibility that it is related to the intervention.
Suspected Unexpected Serious Adverse Reactions (SUSARs)	A SAR, the nature and severity of which is not consistent with the Reference Safety Information (RSI) for the intervention.

*Note: The term 'life-threatening' in the definition of serious refers to an event in which the trial participant was at risk of death at the time of the event or it is suspected that used or continued used of the product would result in the subjects death; it does not refer to an event which hypothetically might have caused death if it were more severe.

- ** Note: Hospitalisation is defined as an inpatient admission, regardless of the length of stay, even if the hospitalisation is a precautionary measure for continued observation. Pre-planned hospitalisation e.g. for pre-existing conditions which have not worsened, or elective procedures, does not constitute an SAE.
- *** Note: other events that may not result in death, are not life-threatening, or do not require hospitalisation, may be considered as an SAE when, based upon appropriate medical judgement, the event may jeopardise the participant and may require medical or surgical intervention to prevent one of the outcomes listed above.

13.2 Trial Specific SAE Reporting Requirements

For this low risk trial there will be no additional SAE reporting requirements to those detailed above. However, all falls, regardless of severity should be reported as an expected adverse event. Falls should be reported within 7 days of the event using the specific form on the REDCap database, but noting that the event does not constitute a serious event.

These should be completed in the participant's notes and on the relevant CRF pages and forwarded to the CTR in the normal timeframes for CRFs.

Participants should be encouraged to email the trial team if they experience any adverse events to the trial email address listed below and this will be recorded by the trial team.

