13.4 Expectedness

The CI (or another delegated appropriately qualified individual) will assess each SAE to perform the assessment of expectedness.

SAEs which add significant information on specificity or severity of a known, already documented adverse event constitute unexpected events. For example, an event more specific or more severe than that described in the protocol is considered unexpected. All AE and SAE reporting relating to falls should be reported as expected unless the person reporting judges that the specific incident is an unforeseen consequence of participating in the intervention.

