13.5.2 The CTR Responsibilities

Following the initial report, all SAEs should be followed up to resolution wherever possible, and further information may be requested by the CTR. For follow-up information, sites to update the initial copy of the SAE form and put a single line through the old information and new information added.

The CTR should continue reporting SAEs until the participant has completed the 12 week follow-up assessment.

Once an SAE is received at the CTR, it will be evaluated by staff at the CTR and sent to the CI (or their delegate) for an assessment of expectedness.

Only reports of related and unexpected SAEs should be submitted to the REC. These should be sent within 15 days of the CI becoming aware of the event.

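### Section 13.2 has every fall reported as expected and noted as not serious on a 7-day form, which contradicts the protocol's own SAE definition and 24-hour rule and lets a serious fall be misfiled

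*Protocol*

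**What the plan says.** Section 13.2 sets a rule specific to falls: "all falls, regardless of severity should be reported as an expected adverse event". It then sets the deadline and the form: "Falls should be reported within 7 days of the event using the specific form on the REDCap database". The same sentence goes on to fix how seriousness is entered on that form: "but noting that the event does not constitute a serious event".

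The rest of section 13 treats seriousness as a matter of outcome:

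- Section 13.1 lists the seriousness criteria, which include death, persistent or significant disability, and "Required hospitalisation or prolongation of existing hospitalisation". The note below the table is broad: "Hospitalisation is defined as an inpatient admission, regardless of the length of stay". Precautionary admissions count. Falls are not exempted.
- The opening of section 13 requires SAEs to reach the CTR within 24 hours of knowledge, "unless the SAE is specified as not requiring immediate reporting (see section 13.2"). The instruction at the front of the protocol sets the same 24 hours for any event in a serious category and has no exemption.
- Section 13.3 requires a causality assessment, and section 13.4 an expectedness assessment, for each SAE.
- Section 13.4 gives expectedness to the CI or a delegate. It then makes falls, whether AE or SAE, expected by default, unless the person reporting judges the incident to be a consequence of the intervention that was not foreseen.
- Section 13.5.2 sets the onward filter: "Only reports of related and unexpected SAEs should be submitted to the REC".

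**The concern.** A site dealing with a fall that ends in admission cannot follow 13.1 and 13.2 together. One makes the event an SAE; the other has it noted as not serious. Which route the site takes determines the reporting deadline, whether a clinician must judge causality, and whether anyone considers onward reporting.

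Falls are the one event type that 13.2 singles out. Table 2 calls them a common symptom in people with PD, and they are also measured as an outcome through the Dresden Falls Questionnaire. If serious falls are misfiled, the SAE listing could understate serious harm in the feasibility data that are meant to inform a full trial.

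**Working it through.** No sample size, power or event count is involved. The check is to follow one case, a fall leading to an inpatient admission, through the text.

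| Question | Following 13.2 | Following 13, 13.1 and 13.4 |
|---|---|---|
| Serious? | No, by the note on the form | Yes, by the admission criterion |
| Deadline | 7 days from the event | 24 hours from knowledge, unless the exemption pointing to 13.2 is applied |
| Causality assessed? | Not required, since 13.3 covers SAEs | Required |
| Expected? | Yes, with no exception stated | Yes by default, with an exception at the reporter's judgement |
| To the REC? | No, since it is not handled as an SAE | Only if related and judged unexpected |

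**Seriousness.** The two columns contradict each other. Section 13.4 refers to SAE reports relating to falls, so the protocol itself accepts that a fall can be serious, as 13.1 implies.

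**Timing.** The exemption in section 13 refers the reader to 13.2 for SAEs that need not be reported immediately. Section 13.2 names only falls, so a site can reasonably conclude that serious falls are the exempt class. Section 13.5.1 does not settle the matter, because its 24-hour form is for events requiring immediate reporting, which is the point in doubt. The two deadlines also start at different moments. For a fall known to the site at once, the windows are 24 hours and 7 × 24 = 168 hours, a difference of 168 − 24 = 144 hours. The gap shrinks as knowledge comes later, and it disappears when the site first learns of the fall 144 hours (6 days) after it happened.

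**Causality.** Under 13.5.1 the PI's seriousness and causality judgements are signed on the SAE form. A fall filed only on the falls form, already noted as not serious, has no point at which the protocol requires either judgement.

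**Expectedness and the REC.** A fall handled as an SAE is expected by default under 13.4, so 13.5.2 keeps it from the REC even when related. It goes forward if the reporter uses the exception. Section 13.2 does not repeat that exception, and 13.4 leaves it to the reporter while otherwise giving expectedness to the CI.

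**The case against.** The best defence is that 13.2 was meant only to add a light route for minor falls. It opens by adding nothing to the SAE requirements already given, which leaves the duties in 13 and 13.1 standing. The instruction at the front of the protocol has no falls exemption, and 13.4 plainly envisages fall SAEs. On that reading the not-serious note applies only to falls that meet no criterion. This is a fair account of what the authors may have intended, and it means the 24-hour route is not closed. But 13.2 does not say so, its severity wording points the other way, and section 13 refers to it for exemptions. The contradiction in the text stands.

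Several stronger readings are tempting and are not supported:

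- *Related serious falls can never reach the REC.* The 13.4 exception lets the reporter classify a fall as unexpected, and 13.5.2 then requires submission. They are withheld by default, not absolutely.
- *The reporting clock is 7 days for all serious falls.* It can become 7 days; another reading keeps it at 24 hours.
- *Section 13.4 contradicts itself on severity, because* "an event more specific or more severe than that described in the protocol is considered unexpected". This is weak. The protocol describes falls at any severity, so no fall exceeds the description, and the falls sentence reads as a specific exception to a general rule.
- *Serious falls go unrecorded.* Every fall is still to be recorded. The risk is misclassification.
- *Declaring falls expected in advance is itself an error.* For an event the protocol calls common in PD, that is a legitimate choice. So is the REC filter.

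**Conclusion.** The point holds as an internal contradiction, and the protocol should be corrected. For a fall meeting any 13.1 criterion, 13.2 conflicts with 13.1 on seriousness, with section 13 and the front of the protocol on timing, and with 13.4 on whether a fall can be an SAE. A site following 13.2 can file such a fall as non-serious without the assessments required for SAEs.

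Its extent is every serious fall. How many there would be cannot be stated, since the protocol gives no fall or admission rate. Whether misfiling occurs depends on which reading site staff adopt. The progression criteria in 5.3 and the analyses in 15.1 are unaffected; the matter is safety reporting and the reliability of the SAE data. The text on who decides expectedness for falls, the CI or the reporter, is also unresolved.

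**What to change.** Reconcile sections 13, 13.1, 13.2 and 13.4:

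- Restrict the 7-day falls form and its not-serious note to falls that meet none of the 13.1 criteria.
- State that a fall meeting any criterion follows the protocol's existing SAE route, with causality assessed.
- Amend the cross-reference in section 13 so that it cannot be read as exempting serious falls.
- State in one consistent way who decides expectedness for falls, and repeat the 13.4 exception in 13.2.

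The default of treating falls as expected may stay. The cost is protocol wording, a seriousness check on the falls form in REDCap, and a few more SAE forms.

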13.3 Causality

Causal relationship will be assessed for the intervention and procedures:

Intervention: SParky Samba intervention

The PI (or another delegated medically qualified doctor from the trial team) will assess each SAE to determine the causal relationship and the Chief Investigator (CI) (or another appropriately qualified member of the Trial Management Group (TMG)) can also provide this assessment where necessary:

Relationship	Description	Reasonable possibility
		that the SAE may have
		been caused by the
		intervention?
Unrelated	There is no evidence of any causal relationship with the	No
	intervention	
Unlikely	There is little evidence to suggest there is a causal	No
	relationship with the intervention (e.g. the event did	
	not occur within a reasonable time after administration	
	of the trial medication). There is another reasonable	
	explanation for the event (e.g. the participant's clinical	
	condition, other concomitant treatment).	
Possible	There is some evidence to suggest a causal relationship	Yes
	with the intervention (e.g. because the event occurs	
	within a reasonable time after administration of the	
	trial medication). However, the influence of other	
	factors may have contributed to the event (e.g. the	
	participant's clinical condition, other concomitant	
	treatments).	
Probable	There is evidence to suggest a causal relationship and	Yes
	the influence of other factors is unlikely.	
Definite	There is clear evidence to suggest a causal relationship	Yes
	and other possible contributing factors can be ruled	
	out.	

The causality assessment given by the PI (or delegate) cannot be downgraded by the CI (or delegate), and in the case of disagreement both opinions will be provided.

13.4 Expectedness

The CI (or another delegated appropriately qualified individual) will assess each SAE to perform the assessment of expectedness.

SAEs which add significant information on specificity or severity of a known, already documented adverse event constitute unexpected events. For example, an event more specific or more severe than that described in the protocol is considered unexpected. All AE and SAE reporting relating to falls should be reported as expected unless the person reporting judges that the specific incident is an unforeseen consequence of participating in the intervention.

13.5 Reporting Procedures

13.5.1 Participating Site Responsibilities

The PI (or delegated appropriately qualified doctor from the trial team) should sign and date the SAE CRF to acknowledge that he/she has performed the seriousness and causality assessments. Investigators should also report SAEs to their own health boards or trust in accordance with local practice.

A completed SAE form for all events requiring immediate reporting should be submitted via email to the CTR within 24 hours of knowledge of the event. A separate form must be used to report each event, irrespective of whether or not the events had the same date of onset.

The participant will be identified only by trial number, age at time of adverse event or partial date of birth (mm/yy) and initials. The participant's name should not be used on any correspondence.

It is also required that sites respond to and clarify any queries raised on any reported SAEs and report any additional information as and when it becomes available through to the resolution of the event. Additionally, the CTR may request additional information relating to any SAEs and the site should provide as much information as is available to them in order to resolve these queries.

Serious Adverse Event (SAE) email address:

[contact]

Serious adverse events should be reported from time of signature of informed consent, throughout the intervention delivery period up to, and including the outcome assessment visit at 12 weeks.

An SAE form is not considered as complete unless the following details are provided:

- Full participant trial number
- An Adverse Event
- A completed assessment of the seriousness, and causality as performed by the PI (or another appropriately medically qualified doctor registered on the delegation log).

If any of these details are missing, the site will be contacted and the information must be provided by the site to the CTR within 24 hours.

All other AEs should be reported on the CRF following the CRF procedure described in Section 16.

13.5.2 The CTR Responsibilities

Following the initial report, all SAEs should be followed up to resolution wherever possible, and further information may be requested by the CTR. For follow-up information, sites to update the initial copy of the SAE form and put a single line through the old information and new information added.

The CTR should continue reporting SAEs until the participant has completed the 12 week follow-up assessment.

Once an SAE is received at the CTR, it will be evaluated by staff at the CTR and sent to the CI (or their delegate) for an assessment of expectedness.

Only reports of related and unexpected SAEs should be submitted to the REC. These should be sent within 15 days of the CI becoming aware of the event.

13.7 Urgent Safety Measures

An Urgent Safety Measure (USM) is an action that the Sponsor, Co-Cls or Site PI may carry out in order to protect the participants of a trial against any immediate hazard to their health or safety. Any USM relating to this trial must be notified to the REC immediately by telephone, and in any event within three days in writing, that such a measure has been taken. USMs reported to the CTR will be handled according to CTR processes.

14 Statistical Considerations

14.1 Randomisation

Participants will be randomised to the intervention or control in a 1:1 ratio, stratified by disease burden (Hoen and Yahr stage). Randomisation will be completed within study REDCap database. Full details of the randomisation procedure will be specified in a separate randomisation plan.

14.2 Blinding

Owing to the nature of the intervention under investigation, this study will remain unblinded.

14.3 Sample Size

As a feasibility study, this has not been powered to detect effects in clinical outcome measures. The recruitment target of 60 has been selected in line with guidance for sample sizes in feasibility studies for 30 participants per group (29). This sample size will allow estimation of recruitment, retention and adherence rates with a 95% binomial confidence interval of no more than plus or minus 13 percentage points irrespective of the point estimate.

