
AE	Adverse Event
AR	Adverse Reaction
CF	Consent Form
CI	Chief Investigator
CRF	Case Report Form
CTR	Centre for Trials Research
cv	Curriculum Vitae
DREFAQ	Dresden Falls Questionnaire
FoG	Freezing of Gait
GCP	Good Clinical Practice
ISF	Investigator Site File
ISRCTN	International Standard Randomised Controlled Trial Number
MoCA	Montreal Cognitive Assessment
NHS	National Health Service
OxPAQ	Oxford Participation and Activities Questionnaire
PD	Parkinson's disease
PDQ-8	Parkinson's Disease Questionnaire 8
PI	Principal Investigator
PIC	Participant Identification Centre
PIS	Participant Information Sheet
PROMS	Patient Reported Outcome Measures
QA	Quality Assurance
QC	Quality control
QoL	Quality of Life
RCT	Randomised Controlled Trial
REC	Research Ethics Committee
SAE	Serious Adverse Event
SOP	Standard Operating Procedure
TIDieR	Template for Intervention Description and Replication
тм	Trial Manager
TMF	Trial Master File

TMG	Trial Management Group	
TSC	Trial Steering Committee	
TUG	Timed Up and Go	
UPDRS	Unified PD Rating Scale	

1 Amendment History

The following amendments and/or administrative changes have been made to this protocol since the implementation of the first approved version.

Amendment No.	Protocol version no.	Date issued	Summary of changes made since previous version

2 Synopsis

Short title	Evaluating the feasibility of a samba percussion intervention for people with			
	Parkinson's disease (PD)			
Acronym	SParky Samba			
Funder and ref.	Jacques and Gloria Gossweiler Foundation			
Trial design	Feasibility Randomised Controlled Trial (RCT)			
Trial participants	Patients with Parkinson's disease (PD)			
Planned sample size	Feasibility RCT, n = 60 (30 in intervention group, 30 in activity as usual)			
Planned number of sites	4			
Inclusion criteria	People diagnosed with PD			
	Age 18 or older			
	Able to provide consent to take part			
Exclusion criteria	Has already taken part in a SParky Samba group			
Intervention duration	12 weeks			
Planned trial period	Planned recruitment time from April 2025 – February 2026			
Primary objectives	Determine feasibility of testing the SParky Samba intervention in a feasibility RCT.			
Secondary objectives	Explore the effect of the SParky Samba intervention as compared to activities as usual across function and wellbeing of people with PD.			
Primary outcomes	 Feasibility of participant recruitment and retention and intervention adherence according to pre-specified criteria. 			

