5.3 Primary Outcome Measure

Feasibility of participant recruitment and retention and intervention adherence according to prespecified criteria

	Progression Criteria				
		Red	Amber	Green	
Recruitment	No. approached willing to participate				
	(number consented/ number				
	approached)	<5%	5-19%	≥20%	
		< 24 in			
	No. recruited	total	25-44	45-60	
Retention	No of participants completing primary				
	end point	<50%	51-89%	≥90%	
	% Participants adherent to the				
Adherence	intervention (as defined in section 11.1)	<50%	51-79%	≥80%	
	% Participants completing at least 90%				
	of available baseline measures	<70%	71-94%	≥95%	
Data	% Participants completing at least 90%				
Completeness	of follow up measures	<50%	51-74%	≥75%	

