5.4 Secondary Outcomes Measures

- Unified PD Rating Scale (UPDRS) (19),
- Freezing of Gait (FOG) Questionnaire (20)
- Dresden Fall Questionnaire (DREFAQ) (21)
- MiniBEST Test (22)
- Montreal Cognitive Assessment (MoCA) short from [Espresso] (23)
- PD Questionnaire 8 (PDQ-8) (24)
- Oxford Participation and Activities Questionnaire (OxPAQ) (25,26)

- Lorig Self Efficacy Scale (26,27)
- Physical Activity Scale for the Elderly (PASE)(28)

6 Trial Design & Setting

This will be a parallel group feasibility RCT of the SParky Samba intervention compared to an activity as usual control group. A recruitment target of 60 people with PD will be randomised 1:1 to intervention or activity as usual. Participants will be recruited from a combination of specialist movement disorder clinics, via the PD specialist nurse network, social media advertising and advertising through local PD focused organisations such as Parkinson's UK Cymru. The SParky Samba intervention will be delivered across three principal community sites in Wales (Cardiff, Llandudno and Fishguard) with possible additional sites in Carmarthen and Chepstow, dependent on external funding. Outcomes will be assessed at baseline (prior to randomisation) and at the end of the 12 week intervention delivery period. Those randomised to the activity as usual group will be able to access SParky Samba after the completion of the 12 week follow-up assessments.

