11.1 SParky Samba Intervention

SParky Samba is a samba-based rhythm/ drumming intervention delivered within the community for people with PD. The setting is determined by local availability of facilities, which are chosen by SParky Samba leaders based on their geographic location and accessibility for group members.

The group is facilitated by either a local Samba musician, or a regular member of the group who has been trained by the musician to deliver SParky Samba sessions. The group size is usually around 8-15 participants but there is no minimum or maximum number of participants required for any given session.

In their first session participants will be offered a choice of instrument that is suitable for their range of motion. This could range across tamborims, Snare drums (Caixa), Agogo bells, Surdos, Ganzás / Chocalho (shakers), Cuíca, Timbal, Pandeiro, and the Repinique.

During each session, participants will be instructed to follow a sequence of rhythms, as guided by the facilitator. Each rhythm is broken down into smaller sections with sub-groups (grouped by instrument) concentrating on their own section before coming together. The band leader often carries a Repinique, as well as using Apitos (whistle) to signal breaks to participants.

Each session will last approximately 60 minutes with time either side for the set-up and break down of instruments and seating.

Participants will be asked to attend as many sessions as possible, ideally weekly over a period of 12 weeks following randomisation. Participants will be encouraged to attend at least 6 consecutive sessions and a minimum of 8 in total (completion of 8 sessions in total will be regarded as adherent to the intervention). The costs of participant travel to attend Sparky Samba sessions will be reimbursed. Alternatively, travel arrangements will be made upfront on behalf of the participant if they prefer.

The PPI Group have been involved in the co-production of patient facing materials and the intervention definition through a series of stakeholder workshops that have informed phase 2 of the trial. The trial team will continue to work with the PPI Group throughout the trial in co-production of documents for publication and an Intervention Manual.

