11.2 Intervention Comparator

Participants randomised to the activity as usual control group will be asked to continue with their normal activities and attend any social or support groups they would normally attend over the 12 weeks. Following completion of the 12-week follow-up assessment they will be offered the opportunity to join their local SParky Samba group.

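### The ±13-point precision bound in section 14.3 does not hold for adherence, which can be measured only in the 30 intervention participants (about ±18 points)

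*Protocol*

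**What the plan says.** Section 14.3 rests the sample size first on cited guidance: "The recruitment target of 60 has been selected in line with guidance for sample sizes in feasibility studies for 30 participants per group (29"). It then states what that size delivers for the three feasibility rates, namely estimation of "recruitment, retention and adherence rates with a 95% binomial confidence interval of no more than plus or minus 13 percentage points", and says that this holds whatever the point estimate.

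The Synopsis gives the arm sizes as "n = 60 (30 in intervention group, 30 in activity as usual"), and section 6 confirms 1:1 randomisation.

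The three rates are defined as follows:

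- **Adherence.** The progression table in 5.3 counts the percentage of participants adherent to the "intervention (as defined in section 11.1"). Section 11.1 makes this a yes/no status per person: "completion of 8 sessions in total will be regarded as adherent to the intervention". Under 11.2, controls "will be asked to continue with their normal activities and attend any social or support groups they would normally attend over the 12 weeks". Section 15.1 describes adherence differently, as a percentage of recommended sessions completed, in either the intervention or a social control.
- **Retention.** Section 15.1 uses everyone recruited as the denominator.
- **Recruitment.** Section 5.3 divides the number consented by the number approached; 15.1 divides by the number eligible.

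**The concern.** One bound is given for three rates that do not share a denominator. A half-width of 13 points at any point estimate needs close to 60 people, but the adherence criterion concerns only the arm that is offered SParky Samba.

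Feasibility is the primary outcome, and adherence is one of its deciding criteria. Under 15.1 an overall green needs every criterion to be green, and one red criterion makes the overall result red. A reader who relies on 14.3 will think the adherence rate is known more precisely than it will be, and will see an adherence result near a cut as firmer than it is.

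**Working it through.** **Inputs.** Total 60 and 30 per arm (Synopsis, 6, 14.3); 95% confidence (14.3); green cut for adherence 80% (5.3). The number approached or eligible is not given in the protocol and is treated below as an assumption.

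**Formula.** Wald half-width = 1.96 × √(p(1 − p)/n), largest at p = 0.5. Exact (Clopper-Pearson) half-widths are given alongside.

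**Step 1: reproduce the stated figure.** With n = 60 and p = 0.5, 1.96 × √(0.25/60) = 12.65 points, which rounds to 13. The exact interval for 30/60 is 36.8% to 63.2%, or ±13.2. The smallest n that gives ±13 by Wald is 57. The figure therefore comes from all 60 participants.

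**Step 2: adherence, n = 30.**

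| Case | Result |
|---|---|
| p = 0.5, Wald | 1.96 × √(0.25/30) = ±17.9 |
| p = 0.5, Wilson | ±16.9 |
| p = 0.5, exact (15/30) | 31.3% to 68.7%, ±18.7 |
| p = 0.8, Wald | 1.96 × √(0.16/30) = ±14.3 |
| 24/30, exact | 61.4% to 92.3% |

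None of the three methods gives 13 at p = 0.5. The Wald half-width is 13 or less only where p(1 − p) ≤ 30 × (0.13/1.96)² = 0.132, that is, p of about 84% or more, or about 16% or less. With 30 people the first attainable high value is 26/30 (±12.2); 25/30 gives ±13.3. The error factor is √(60/30) = √2.

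**Step 3: retention, n = 60.** ±12.7 (Wald) or ±13.2 (exact) at p = 0.5. The stated bound is right to the nearest point.

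**Step 4: recruitment.** The denominator, approached or eligible, cannot be smaller than the number who consent. If 60 consent it is at least 60, so the Wald half-width is at most 12.7 at any point estimate. For illustration only:

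- 60 of an assumed 300 (20%): 1.96 × √(0.2 × 0.8/300) = ±4.5.
- 60 of an assumed 1,200 (5%): 1.96 × √(0.05 × 0.95/1200) = ±1.2.

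The bound is not breached, but it says little about the precision to expect.

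**The case against.** The best defence of 60 for adherence is that 15.1 refers to intervention or social control sessions, and section 12 plans to collect adherence data for the comparator too. On that reading both arms contribute. This does not rescue the figure. A percentage of sessions completed is not a binomial proportion of participants, so a binomial interval would not apply to it. Section 11.2 prescribes no sessions for controls. The traffic light in 15.1 is judged against the criteria in 5.3, which point to 11.1. What stands is that the protocol carries two descriptions of adherence, and they need reconciling.

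A reader might also infer more than the document supports:

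- *That ±13 is wrong for all three rates.* It is correct for retention and not exceeded for recruitment. The phrase about any point estimate can stay for those two.
- *That the sample size loses its justification.* Section 14.3 first rests the 60 on guidance for 30 per group; the precision sentence describes that size and does not derive it.
- *That red, amber or green calls would change.* Sections 5.3 and 15.1 compare observed values with fixed cuts, and no rule uses a confidence interval. The harm is limited to how precisely adherence is believed to be known.

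**Conclusion.** The stated bound is false for adherence as the progression criterion defines it. The worst case is about ±18 points (17.9 Wald, 18.7 exact) against the stated 13, an understatement of about 5 points. At the green cut the Wald half-width of 14.3 is still above 13.

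This assumes that the target of 60 is met, with 30 per arm, and that all 30 intervention participants are in the adherence denominator. With fewer recruits both figures widen: at 45 in total, the bottom of the green band for numbers recruited in 5.3, retention would be ±14.6 (Wald, n = 45) and adherence about ±20.9 (Wald, n = 22). The error is one of stated precision for a go/no-go criterion; it does not affect the analysis or the size of the trial.

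**What to change.** Restate the precision sentence in 14.3 by outcome:

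- Retention: at most about ±13 points, n = 60 (±13.2 exact).
- Adherence: at most about ±18 points (±19 exact), n = 30, intervention arm only.
- Recruitment: based on the number approached or eligible. If an example is wanted, label it as an assumption, such as ±4.5 points if 60 of an assumed 300 consent.

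Name the interval method, so that the Wald and exact figures are not mixed.

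In 15.1, bring two definitions into line with the rest of the protocol. Adherence as a percentage of intervention or social control sessions should be reconciled with the per-participant definition in 5.3 and 11.1, and the recruitment denominator (eligible) with that in 5.3 (approached).

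The cost is protocol wording only, and one stated figure becomes less favourable. The sample size, data collection and progression cuts do not change.
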